12.2	Pediatric Populations.....	45
13.	PUBLICATION OF RESEARCH FINDINGS	46
14.	REFERENCES	47

APPENDICES

I.	MODEL INFORMED CONSENT	50
II.	NEUROPSYCHOLOGICAL SCREENING FORM	62

SYNOPSIS

Study Title

Dietary treatment of Glucose Transporter Type 1 Deficiency (G1D)

Objectives

Primary Objectives: To evaluate the impact of triheptanoin (C7 oil; C7) supplementation on measures of neuropsychological function primarily indicative of attention in G1D subjects receiving normal diet.

Secondary Objectives: 1. To evaluate the effect of C7 supplementation of a regular diet on a EEG activity in addition to IQ, language, working memory, processing speed, emotional and behavioral functioning, ataxia, and other neuropsychological and neurological performance indices in children and adults genetically diagnosed with G1D receiving a regular diet at enrolment. 2. To evaluate the safety of C7 supplementation in pediatric and adult subjects diagnosed with G1D on normal diet over a 6 month treatment period.

Design and Outcomes

This is a single-site, open-label, phase II trial of C7 in subjects diagnosed with the most common (epileptic) form of G1D, on no dietary therapy (i.e., consuming a normal diet, unchanged for this study other than for the replacement of some of the diet fat with C7), to explore the feasibility and impact of anaplerotic therapy (C7 dietary supplementation) in G1D using outcome measures that closely trace the disease process. The primary outcome measure will be attention, as measured by performance on a computerized neuropsychological measure as described in section 6.3.9. Attention is a core cognitive function that permits access to other areas of cognition and is commonly impaired in association with seizure disorders. Existing research has indicated that dietary interventions have the potential to promote attention functioning in children with G1D (26, 27). The secondary outcome measures are: 1. Changes in other aspects of neuropsychological (IQ, language, working memory, processing speed, emotional and behavioral functioning) and neurological performance, including ataxia and global impression scales. 2. EEG changes (as precisely defined below) during C7 treatment. 3. Safety of 6 month supplementation with C7 as measured by the absence of clinically significant changes in standard laboratory measures (blood cell count, blood electrolytes, AST, ALT, blood urea nitrogen, creatinine, lipid panel, plasma glucose and Beta-hydroxybutyric acid).

Interventions and Duration

This is an open-label, single arm trial of orally-administered C7 in G1D. Subjects will replace a fixed percentage of their daily caloric intake (based on the results of Protocol 1) with C7 for 6 months, undergo full evaluation and discontinuation of treatment at a 6 month visit, and return for an off-treatment follow up visit 3 months after C7 oil discontinuation, for total duration of participation of 9 months. Subjects will undergo

treatment initiation on a 24-hour inpatient basis. During that 24-hr inpatient treatment initiation, subjects will have continuous EEG both to monitor for real-time seizure activity (for safety) and to determine EEG changes (secondary outcome) before, during, and after treatment initiation. Subjects will undergo clinical evaluation, comprehensive blood work, ataxia scale rating, EEG, and neuropsychological testing at baseline, 6 months, and 9 months.

Important: As described in the Proposal and in (1), C7 is always administered as a **replacement** (nor as a source of extra calories for an otherwise unchanged regular diet) to a fraction of the daily calories that are normally consumed by each subject via other nutrients. As such, there is **no caloric impact** of C7 (i.e., the calories that a subject will consume remain unchanged by the addition of C7 to the diet to replace other nutrients – predominantly fat).

Sample Size and Population

Forty-five subjects receiving no dietary therapy (i.e., consuming a normal diet) with a proven (genetically determined) G1D diagnosis will be enrolled. Subjects may be male or female, between the ages of 2 and 35 years old (N=15 per age group: 2 to 6, 7-11, and 12-35 years old), and must be willing to provide assent if they are of age 10-17. Subjects may be English or Spanish speaking. Subjects may be currently taking anticonvulsants or other medications. Subjects must agree not to change their dietary therapy during the trial without consulting with the study team. Subjects must have evidence of abnormal EEG in the last 36 months.

1. STUDY OBJECTIVES

1.1. The main hypotheses tested are:

- C7 positively affects neuropsychological indices (sustained attention, IQ, language, working memory, processing speed, emotional functioning, adaptive behavior functioning, and quality of life indicators) and neurological performance, such as ataxia, in G1D.

1.2. The secondary hypotheses tested are:

- C7 provides a spectrum of short-term (hours to days) and long-term (over 6 months) benefits in subjects with G1D, defined as a decrease in abnormal EEG activity both in the acute and long-term, as measured by the change in EEG from pre-C7 baseline. These changes in EEG activity are defined and measured as specified below.
- C7 supplementation is safe when used over a long term (6 months), as measured by the absence of clinically significant changes in standard laboratory measures (blood cell count, blood electrolytes, AST, ALT, blood urea nitrogen, creatinine, lipid panel, plasma glucose, and beta-hydroxybutyric acid).

2. BACKGROUND

2.1. Rationale

Glucose transporter deficiency type 1 (G1D), a prototypic glycolytic defect that impairs the first step of glucose metabolism, was first described in 1991 and is caused by haploinsufficiency of the blood brain barrier and astrocyte glucose transporter (2-4). In its most common form, G1D leads to epilepsy and intellectual discapacity. Associated features include microcephaly (signifying limited brain growth) and movement incoordination (ataxia). There is no known alteration of systemic carbohydrate metabolism.

Some manifestations of G1D are treatable in a significant fraction of patients: In ~2/3 of over 100 subjects that we have cared for over the years, a ketogenic diet has been efficacious for seizure control but without significantly impacting intellectual discapacity or ataxia ((5) and PI observations). Therefore, G1D is at least partially responsive to the alternative fuels generated by the diet in a fraction of patients, namely even-carbon-number fatty acids and ketone bodies (3). We currently care for well over 100 G1D genetically-confirmed subjects, representing ~40% of all North American and ~10% of European subjects either reported or genotyped (often by us (6) under our NIH CETT Program for G1D) and we have elucidated the principal brain metabolic pathways in G1D (7). Although much work remains to be carried out to fully understand the biochemistry of the disorder, significant progress has been made in G1D, such that we believe that the finding of enhanced anaplerosis after administration of the C7 constituent heptanoate and related indicators of tricarboxylic acid (TCA) cycle stimulation (8) warrants the trial of anaplerotic therapy at this time in this disease. An additional sense of urgency is imposed by the potential window of opportunity that closes once the child brain matures.

We have established the dosing, tolerability, and safety profile of triheptanoin in adults in a broad variety of inherited carbohydrate and lipid metabolic disorders (of which G1D is a part) (9-13) (FDA IND 59303: "Dietary therapy for inherited disorders of mitochondrial fat oxidation, glycogenoses and mitochondrial myopathies", responsible investigator [name] and subsequent expansion to "glycolytic defects" and cross-referencing with responsible investigator [name]). The C7 triglyceride has no discernible effects on normal metabolism as assessed by comprehensive analytical methods. However, this has not been sufficiently replicated in G1D. The goal of the accompanying **Protocol 1** is thus to determine the maximum tolerable dose (MTD) and safety profile of triheptanoin in pediatric G1D patients. While there are no significant natural sources of triheptanoin or odd-carbon number fatty acids in nature, triheptanoin is available commercially for cosmetic and food industry applications. C7 is a colorless and tasteless oil.

Forty-five subjects with G1D and currently receiving no dietary therapy diet will participate. After baseline measurements of common blood work analytes, neuropsychological performance, EEG, blood ketone body levels, blood anaplerotic precursor levels and neurological performance, subjects will be given triheptanoin at the MTD (i.e., dosed by individual daily caloric intake), divided in 4 daily fractionated doses.

All subjects will take triheptanoin daily for 6 months. Subjects will return for clinical evaluations, repeat blood work, and neuropsychological testing at this time point, will be discontinued from the oil at this visit, and returned to their usual diet. Subjects will also repeat EEG at this visit. At 3 months after oil discontinuation, subjects will return for a final clinical evaluation, blood work, EEG, and neuropsychological testing.

Rationale for attention functioning as primary outcome: Attention is a core cognitive function that permits access to other areas of cognition and is commonly impaired in association with seizure disorders. Existing research has indicated that dietary interventions have the potential to promote attention functioning in children with G1D (26, 27). With regard to long-term outcomes, research in the field of childhood absence epilepsy has shown that even after attaining seizure freedom, attention deficits may remain (28). In other words, even normal EEG findings may not correspond to functional neuropsychological improvements. These findings in the field of childhood absence epilepsy are significant for the present study given that EEG seizures are more common than observable seizures in children with G1D. Again, attention is a core cognitive function that permits access to other areas of cognition (including language) and is commonly impaired in association with seizure disorders. For all of these reasons, attention functioning as measured by neuropsychological testing (described below in 6.3.9) may be a more relevant primary outcome for the present study than EEG findings. Precedent for neuropsychological ratings as a primary outcome in epilepsy exists. For example, see <https://clinicaltrials.gov/ct2/show/NCT02127918>

Rationale for EEG as secondary outcome: As explained below, EEG seizures in G1D (which are generally defined clinically in idiopathic absence epilepsy as a generalized spike-wave episode lasting over 3.0 s) are more frequent than observable seizures (see also (1) for details) and improvement in EEG outcome (as independently defined for that article) was correlated with 1) improved language functioning, 2) improved cerebral metabolic rate for some subjects, 3) improved quality of life as demonstrated by patient and caretaker reports (see the proposal for details). Thus, EEG is potentially a clinically meaningful outcome that may correlate with patient benefit and disease burden reduction (1).

This study will define meaningful outcome measures for G1D. Based on preliminary evidence, C7 oil therapy may improve important symptoms of G1D (seizures, ataxia, and neurocognitive deficits). Moreover, in contrast to the strict and often unsatisfactory ketogenic diet commonly used for G1D, addition of C7 to

a regular diet represents a simpler treatment that may facilitate compliance, and potentially lead to improved outcomes. Additionally, due to the differential metabolic effects of C7 relative to the ketogenic diet, there is potential for greater neurological and cognitive benefits to subjects than with the ketogenic diet alone.

Establishing long-term safety and tolerability of C7 in children is critical, as many epilepsies manifest in childhood and can negatively impact brain development. By providing a treatment in early childhood, it may be possible to avoid the deleterious effects of chronic, medication-refractory seizures in G1D patients.

2.2 Supporting Data

There is evidence of beneficial effects of C7 metabolism on the TCA cycle G1D (8). This evidence stems from our work in the G1D mouse model via ¹³C nuclear magnetic resonance (NMR) spectroscopy and mass spectrometry. Open-label treatment using triheptanoin has been pioneered by us and others in several disorders characterized by impaired anaplerosis (9, 11, 12, 14), proving safe, tolerable and efficacious.

C7 dosing will adhere to the MTD determined in Protocol 1. The dosing, tolerability, and safety profile of triheptanoin has been documented in other disorders (9, 11, 12, 14). Therapeutic response is seen at 35% of the daily caloric needs supplied by C7 oil, and 14 years of experience administering C7 has elicited no serious adverse events. However, side effects of stomach upset/ diarrhea, nausea, and mild weight gain have been observed. Because C7 oil is a fat, it is possible that subjects will experience changes in lipid levels, cholesterol, and triglycerides, but these changes have not been observed.

3. STUDY DESIGN

This is an open-label, phase II trial of C7 in subjects with G1D.

Forty-five subjects with G1D receiving a modified atkins diet or a normal diet will be enrolled. Subjects will undergo all baseline and follow-up clinic procedures in the Neurology Outpatient Clinic located in the Children's Medical Center Ambulatory Care Pavilion. Inpatient procedures including blood draws will be completed in the Children's Medical Center Epilepsy Monitoring Unit (EMU). These facilities can accept adults as well as children subjects.

Evaluation of outcome measures will be accomplished at the pre- and post-baseline assessments, 6 month post-treatment and 9 month off-treatment time points by comparing baseline, post-treatment, and endpoint measures. Analyses of changes in comprehensive blood work and side effects over time will help ensure further safety and tolerability of C7 oil at the specified dose; improvement in ataxia rating scale, EEG, clinical evaluation, and neuropsychological testing will confirm the use of the clinical measures to assess outcomes.

Neuropsychological testing at the 6-month time point is designed to capture changes in neuropsychological functioning secondary to oil treatment. Testing again at the 9-month time point is designed to assess whether those changes persist for at least the short term (3 months after discontinuation of C7 oil). Most of the measures have alternate forms that may be utilized to minimize practice effects between the 6-month and 9-month time points, or they have shown not to demonstrate practice effects over a 3-month timeframe. As the IQ measures do not have alternate forms and likely are more sensitive to practice effects over that 3-month timeframe, we will not be conducting a 6-month administration of those measures in order to obtain an optimally valid estimate of intellectual functioning at the 9-month time point.

To address the potential circumstance that C7 may be associated or coincide with an increase in clinical seizure frequency between visits, an additional optional procedure will include the performance of a routine outpatient clinical EEG. This procedure will be obtained and reported locally (i.e., in the area of patient residence) in an accredited clinical facility and the report forwarded to the M.D. investigators for decision and intervention as detailed below.

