5. STUDY INTERVENTIONS

5.1. Interventions, Administration, and Duration

5.1.1. Triheptanoin: A triglyceride oil containing three odd-carbon chain-length fatty acids (i.e., a triglyceride of 7-carbon heptanoic acid) manufactured for food applications. Triheptanoin will be taken 4 times per day (approximately every 6 hours: prior to breakfast, lunch and dinner and a mid-afternoon snack) by mouth. It is dosed 4 times per day, divided evenly. Subjects will receive supplementation at the maximum tolerable dose (MTD) determined in Protocol 1 (either 35%, 40%, or 45% of daily caloric intake). Subjects who experience acute gastrointestinal distress (nausea, mild stomach upset, mild diarrhea) may decrease the dose to 50% for two days, then increase the dose over the course of less than a week (in a manner similar to what is described in Protocol 1) until they reach the intended dose. Subjects who are unable to tolerate the maximum tolerable dose will be discontinued from the study. The oil

should be taken approximately one hour before meals, and will be mixed with fat-free, sugar-free yogurt or pudding for administration.

- 5.1.2. Forty-five subjects will be enrolled in a 6 month on/3 month off treatment trial of triheptanoin. Initiation of triheptanoin will be done in the Children's Medical Center Dallas Epilepsy Monitoring Unit.
- 5.1.3. Subjects will not be required to stop other medications. Subjects will be directed to maintain their usual medications, including rescue seizure medications, as necessary for the course of the study. Subjects may have any clinical medical records transferred back to their referring physician at completion of the study.

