5.3. Concomitant Interventions

- 5.3.1. Required Interventions: There are no additional required interventions.
- 5.3.2. Prohibited Interventions: Subjects are prohibited from starting or changing dietary therapy or other oil-based dietary modifications (including ketogenic diet or medium chain triglyceride therapy) while on study protocol. Subjects who feel this change is necessary will be withdrawn from the study for their own protection.
- 5.3.3. Precautionary interventions: [name] or M.D. co-investigator may direct subjects to adjust the dosing of their oil if necessary for tolerability. If subjects experience acute gastrointestinal distress by self-report during treatment initiation, the amount of oil administered will be decreased to 50% of the dose for 2 days, then gradually increased over less than a week until the desired dose is reached. Subjects who are unable to tolerate the maximum tolerable dose of oil will be discontinued from the trial. If subjects experience gastrointestinal distress during the 6 months of treatment (post treatment initiation), the amount of C7 oil will also be decreased as above. Subjects unable to tolerate a return to the required dose will be discontinued from the study. A dietitian will also be available to provide nutritional counseling for subjects who are having difficulties adjusting to the oil, as experience has shown that mixing the C7 oil with an emulsifier, such as yogurt, and other simple dietary interventions can effectively and permanently improve tolerability (based on our previous experience with G1D (1)).
- 5.3.4. Drug treatments during C7 consumption: G1D patients will generally not need to change any concomitant drug treatment as part of this study. Such changes may be initiated by outside local neurologists or by M.D. investigators in this study and prompted by increased seizure frequency or unexpected drug toxicity. While participants will be screened for a stable drug regimen (see Exclusion Criteria) and recognizing that changes in such therapy may occur, the following scenarios will be entertained:

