7. MANAGEMENT OF ADVERSE EXPERIENCES

Previous experience with C7 oil in different populations has yielded no serious adverse effects. Due to the limited nature of the use of C7 oil, there are no definitive data available on how frequent the following side effects occur.

Diarrhea: Subjects who experience diarrhea may be instructed to increase the amount of fiber consumed with each meal. In addition, C7 will be administered in a fat free, sugar free food item, such as yogurt or pudding, and subjects are instructed to consume this food over 30 minutes in order to minimize diarrhea. Subjects who cannot tolerate the maximum tolerable dose will be discontinued from the study.

Stomach pain: Subjects who experience stomach pain at treatment initiation may, at the direction of [name] or M.D. co-investigator, reduce the dose of C7 oil to 50% for 2 days, then increase the daily dose back to the recommended level within a week. If subjects cannot tolerate the recommended dose, they will be discontinued from the study.

Weight gain: Subjects who experience weight gain (defined as any weight gain greater than 5% of the total body weight expected if the individual percentile were followed in the standard weight growth curve; CDC Standard Growth Curves, 2001) will be re-c counseled about the dietary changes recommended while taking the C7 oil supplement. Subjects will have a dietitian consult prior to treatment initiation and during treatment initiation, to discuss these changes (primarily reduction in other dietary fat). If subjects continue to experience weight gain, they will undergo a dietary assessment. If subjects have made recommended changes and continue to gain weight, they will be removed from the study and an adverse event will be reported.

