8. CRITERIA FOR INTERVENTION DISCONTINUATION

Triheptanoin supplementation will be discontinued if any of the following occur:

- Any of the cited or other adverse experiences become intolerable to the subject
- Metabolic syndrome develops as assessed by glucose and lipid profiles
- Any elevation above laboratory normal range in hepatic transaminases or creatinine is noted
- Any clinically relevant blood cell count abnormality develops
- Non-compliance occurs
- Severe intercurrent illnesses take place

Subjects who discontinue due to the above reasons will be asked to return for a final research visit to complete exit procedures and receive referrals for ongoing care if necessary. Subjects who are discontinued due to adverse events will be followed via daily, alternate-day or weekly phone calls to assess resolution of the adverse event.

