9. STATISTICAL CONSIDERATIONS

9.1. General Design Issues

In the proposed single-arm phase II trial, we define favorable impact on the neurocognitive outcome as at least 0.5 standard deviation (SD) improvement in performance on attention measures (measured as described above) after administration of C7. That is, impact on the outcome is determined by whether a treatment causes at least 0.5 SD improvement on the primary attention measure for that age group in a single arm trial and the interest is **primarily focused on reaching a decision on whether to progress with C7 to a future larger trial**. (Note: The SD is a normative parameter provided with the testing instruments). The evidence to make this decision is evaluated by testing the null hypothesis that the true efficacy rate is less than or equal to some pre-specified value. It is desirable to achieve this goal whilst minimizing the number of subjects exposed to a novel agent. Here, we use the Simon's optimal two-stage design that yields the smallest expected sample size when the null hypothesis is true.

We apply Simon's optimal two-stage design (24) using as primary outcome attention performance for each of three age groups. At least 0.5 SD improvement in performance on the primary attention measure after the administration of C7 is considered a favorable outcome. The measurement of 0.5 SD improvement is commonly accepted as the cutoff for a minimally clinically important difference, as described in various studies (e.g., 32, 33).

This protocol will yield data that allow a clear **go/ no-go decision** regarding whether C7 should proceed to an efficacy trial:

- If a favorable outcome occurs in less than 50% of subjects, we will recommend that C7 not proceed to an efficacy trial.
- If a favorable outcome occurs in at least 80% of subjects, we will recommend that C7 proceed to an efficacy trial.

The sample size estimation for this optimal two-stage design is given in Section 9.3.

If an intermediate number of subjects (51 – 79%) exhibit a favorable primary attention outcome, the rest of outcomes, including the long-term, 6-month responses, will be considered for the go/ no-go decision on the basis of impact on these outcomes and the disease process, in addition to tolerability and safety indicators.

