Although a variety of designs were considered, including crossover designs for non-ketogenic diet subjects and randomization to C7 or ketogenic diet, several factors contributed to the development of an open-label design. The G1D population, while hypothesized to be greater than previously realized, is currently a relatively small population and the number of patients needed to adequately power a cross over study could be difficult to recruit. This holds true for a head to head comparison of C7 and ketogenic diet, although the increasing availability of genomic testing may increase the available population in the next few years. Finally, and most importantly, the safety and tolerability of C7 has not been rigorously proven in G1D. Therefore, this issue needs to be addressed before entering into advanced clinical trials.

A six-month, on-supplement follow up time period was chosen in order to provide long-term safety and tolerability data for triheptanoin. Additionally, we consulted with [name] (co-investigator), an established pediatric neuropsychologist expert in G1D. It is general practice to wait a minimum of 6 months after ischemic insult to the brain (such as traumatic brain injury or stroke) before assessing neurocognitive changes. This time period is consistent with how long it takes the brain to demonstrate performance improvement after these insults. Because chronic seizures can also induce long-term brain changes, 6 months was chosen to allow sufficient time for the brain to exhibit improvement that could be captured by the outcome measure tools.

The three-month exit visit allows us to assess whether changes in brain wave activity and other neurocognitive measures persist after withdrawal of oil.

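### Side effects over time are used to support tolerability, but subjects who cannot tolerate the dose leave the study, and no planned analysis keeps them in the denominator

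*Combined protocol and SAP*

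**What the plan says.** **Where tolerability is drawn from.** Section 3 names laboratory changes together with side effects as the basis, and states that "side effects over time will help ensure further safety and tolerability of C7 oil at the specified dose". Section 9.5 examines changes in safety over time by GEE, gives baseline, 6 months and 9 months as the analysis times, and justifies GEE partly by its robustness to random missingness. Its one sentence on multiple imputation stands under the primary aim.

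**Who leaves.**
- Section 5.1.1: "Subjects who are unable to tolerate the maximum tolerable dose will be discontinued from the study".
- Section 5.3.3, for gastrointestinal distress during the six months: "Subjects unable to tolerate a return to the required dose will be discontinued from the study".
- Section 7, under diarrhea: "Subjects who cannot tolerate the maximum tolerable dose will be discontinued from the study".
- Section 8 also ends C7 if "Any of the cited or other adverse experiences become intolerable to the subject" or if "Any elevation above laboratory normal range in hepatic transaminases or creatinine is noted".
- Section 6.2.3 asks early stoppers for one exit visit, at which study participation ends.

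**What rests on tolerability.** Section 9.1 gives as its leading reason for an open-label design that "the safety and tolerability of C7 has not been rigorously proven in G1D". For an intermediate attention result (51 to 79%), it makes the go/no-go decision on the other outcomes "in addition to tolerability and safety indicators". Those indicators are not defined. Section 9.2.2.3 defines safety by laboratory measures and the VA Toxicity Scale. Neither 9.2 nor 9.5 contains a rate of stopping for intolerance, a denominator of all starters, or a rule for the later ratings of subjects who were removed.

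**The concern.** A subject who is removed because of side effects gives no on-oil ratings after the exit visit. The missingness is therefore caused by the quantity under study. It is not the random missingness that 9.5 relies on, so the planned GEE does not correct for it. A comparison of later with earlier ratings sets a tolerant remainder against everyone who started. Section 8 can act on the laboratory trend in the same way, because subjects with raised transaminases or creatinine are taken off C7.

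At stake is the reading of tolerability in the intermediate go/no-go band and in planning a later trial. A favourable trend could be taken as evidence that the assigned dose is tolerated when part of it reflects who was left to rate. The number that a planner needs, the share of starters who could not stay on the assigned dose, is not among the planned results.

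**Working it through.** **1. The plan's own figures (section 9.3).** The only related design figure is the dropout allowance. The Simon design (stop at 4 or fewer of 7; fail at 8 or fewer of 13; null 50%, alternative 80%) reproduces: exact type I error 0.0992 and power 0.818, against a stated 0.1 and 80%. Each age group recruits 15 to leave 13, so the implied loss is 2 per group, or 3 × 2 = 6 of 45, leaving 39. The plan does not split dropout by reason and gives no side-effect rate.

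**2. Formula.** Let N subjects start, let k have side effects early on, let d of those k be removed for intolerance, and let nobody's side-effect status change. Then

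- early prevalence = k/N
- apparent later prevalence = (k − d)/(N − d)

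**3. Numbers, with N = 45.** The starting prevalence is assumed and shown over a range. The value d = 6 assigns every planned loss to intolerance; d = 3 assigns half, with no other losses.

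| Assumed k/N | d = 0 | d = 3 | d = 6 |
|---|---|---|---|
| 9/45 = 20% | 20% | 6/42 = 14.3% | 3/39 = 7.7% |
| 18/45 = 40% | 40% | 15/42 = 35.7% | 12/39 = 30.8% |
| 27/45 = 60% | 60% | 24/42 = 57.1% | 21/39 = 53.8% |

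The apparent fall runs from about 3 points (60% to 57.1%) to about 12 points (20% to 7.7%), with no true change in anyone. If all 45 stay in the denominator and removals for intolerance count as not tolerated, the figures stay at 20%, 40% and 60%.

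**4. Condition on the direction.** The fall requires that other losses be unrelated to side effects. If 3 subjects leave for intolerance and 3 others leave who all happen to be free of side effects, 60% becomes (27 − 3)/(45 − 6) = 24/39 = 61.5%, a slight rise.

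**5. Link to the planned times.** Of the three times in 9.5, only month 6 is on oil; baseline precedes C7 and month 9 is off oil. In that analysis the effect would appear as too small a rise from baseline. In the monthly call data it would appear as a fall.

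**6. Precision of the direct measure.** If all 6 planned losses were for intolerance, the rate among starters would be 6/45 = 13.3% (exact 95% CI 5.1 to 26.8%). In one age group, 2/15 = 13.3% (1.7 to 40.5%).

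**The case against.** The strongest reply is that intolerant subjects do not vanish. Early stoppers are asked for an exit visit (6.2.3, 8), those stopped for adverse events are followed by phone (8), all adverse effects are recorded (10.4.2), and side effects are assessed at the monthly calls (6.2). In an open-label trial of 45, the investigators would know of these withdrawals. This stands: the information exists. What is missing is a prespecified summary that uses it.

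Tolerability is also not the main decision variable. It enters go/no-go only between 51 and 79%, as one input among several, and finding the tolerable dose is the task of Protocol 1. This too stands, and it limits the weight of the point.

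A reader might infer more than the documents support:

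- **That C7 is bound to look better tolerated through selection alone.** This needs at least one removal for intolerance, and no rate is given. Section 5.1.4 says that gastrointestinal effects usually resolve after the dose is halved and raised again, so a fall could also be real adaptation.
- **That the side-effect curve is the plan's sole measure of tolerability.** Section 3 says only that such analyses will help, and nothing says that withdrawals will be ignored.
- **That the distortion is large, for example 40% falling to 25%.** That requires 9 of 45 to leave for intolerance: (18 − 9)/(45 − 9) = 9/36. This is 20% of starters, more than the plan's 15% allowance for dropout of all causes.
- **That 6/45 should be contrasted with 0/39 among those still on oil.** The second figure is zero by definition, since it counts stoppers among those who did not stop.

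Part of the text between 9.3 and 9.5, on the monitoring committee, could not be seen. Whether it provides for review of withdrawals is unknown.

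**Conclusion.** The point holds as a gap in the analysis plan. Followed as written, the trend in side effects is conditional on remaining in the study, and it is biased toward good tolerability whenever subjects leave for intolerance and other losses are unrelated to side effects. Under the plan's own loss of 6 of 45, all assigned to intolerance, an assumed 40% prevalence would appear as 30.8%; with 3 such losses, 35.7%; with none, 40%. These are illustrations. The starting prevalence and the share of dropout due to intolerance are both assumed, and the true size cannot be derived from the documents.

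The primary attention analysis is outside this point. The change is worth making because section 9.1 relies on tolerability without defining it, and because a proportion among all starters is simple and free of this selection.

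**What to change.** 1. In 9.2.2.3 and 9.5, add a secondary outcome: the proportion of all subjects who took at least one dose of C7 who, by month 6, stopped C7 or could not return to the assigned dose because of side effects. Give exact 95% confidence intervals overall and per age group. Report alongside it the proportion with any dose reduction for side effects. With 15 per group the group intervals will be wide, so the overall figure should carry the interpretation.
2. In 9.1, name this proportion as the tolerability indicator for the intermediate band.
3. Present side effects by visit with removals for intolerance counted as not tolerated at later on-oil visits. Do not carry the last rating forward: sections 5.1.1, 5.3.3 and 7 provide for a reduction to 50% before removal, so that rating may have been made at a reduced dose.
4. Label the GEE trend as conditional on remaining on C7.

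**Cost.** A minor protocol and SAP amendment with IRB review (section 11.1), a case report form field for the reason for stopping or reducing the dose, and acceptance of a tolerability figure that may look less favourable. No extra visits are needed, and no dosing or stopping rule changes.
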